An article has been published in *British Journal of Nursing* (2) about the consensus guidelines to encourage nurses to choose ostomy products based on assessment of the individual body profile of the user. The paper shows how the consensus guidelines were developed and presents concept and purpose of the 6 steps in the Body Assessment Tool in hope of providing nurses a more structured and "right from the start" approach when choosing ostomy products. However, the Body Assessment Tool needs to be evaluated in clinical settings to document the usability among nurses and to explore its impact on selection of ostomy product(s) together with a potential improvement of leakage incidences and the user's leakage-related quality of life using the validated OLI score (Ostomy Leakage Impact Tool)(3).

Furthermore, it is of interest to explore usability of The Body Assessment Tool in the group of newly stoma patients (i.e. newly patient discharged (NPD)) as they may have a potentially larger extent of change of their peristomal body profile post-surgery compared to experienced people with a stoma (i.e. veterans). A subgroup of NPDs will therefore be recruited at one clinical site,
Meilahden tornisairaala, Finland

2. Hypothesis

The hypothesis is that with the Body Assessment Tool in combination with the use of the current guidelines and practices, nurses will be able in a standardised way to choose the most appropriate ostomy product(s) for the given user and may thereby help improving the QoL of the user by reducing the users concerns about leakage and preventing the incidences of leakage.

3. Objectives

3.1. The primary objective

- To evaluate the usability of the 6- step Body Assessment Tool in clinical settings (performed by the nurse) – see appendix A. For the usability evaluation a questionnaire has been prepared, the Nurse Evaluation Form – see appendix B.

3.2. The secondary objectives

- To explore if the use of Body Assessment Tool and related change of ostomy product(s) have an impact on the leakage associated QoL (based on the OLI score)- see appendix C. The OLI score includes three domain scores:
 - emotional impact
 - usual and social activities
 - coping and in control
- To evaluate the incidences of leakage before and after change of ostomy product(s) (the question will be included in a leakage questionnaire in addition to the OLI score – see appendix D).

4. Study design

The study is a 1-sequential, 1-arm, non-randomised, non-blinded, multi-center (between 20 to 40 sites in total) non-interventional 4-5-week clinical investigation in which the Body Assessment Tool will be evaluated for its usability by ostomy nurses using the Nurse Evaluation Form and to explore if the change of ostomy product(s) can reduce the user's concerns about leakage and have a positive impact on QoL related to leakage (estimated by the OLI score). For evaluation of the number of leakage incidences the last 7 days pre- and post-change of ostomy products a questionnaire is prepared including a definition of leakage and images for support.

Blinding is not applicable as change of ostomy product(s) cannot be blinded for either the user or nurse. Randomization is not applicable as there will be no comparison to a specific ostomy product or control group. The subjects will change their ostomy product(s) based on their individual body profile assessment and the selection of ostomy products will vary in between subjects and will not be dictated by this protocol.

The NPD subgroup will follow the same protocol as the veterans. However, the data (NPDs vs. veterans) will not be compared due the potentially difference in the change of peristomal body profile. The NPD data will be regarded and handled as exploratory.

All assessments will be based on questionnaires either completed by the nurse or user. Usability data will only be analyzed using descriptive methods. Whereas the OLI score results will be analyzed by descriptive methods (sub-questions in OLI score) and paired t-test (domain scores). The number of leakage episodes will be analyzed by paired t-test.

The study will include 1 visit at the clinic and at least 1 phone call visit to the user (end-of study phone visit). The number of phone calls will vary depending on the user's need for support.

Prior to screening the nurse identifies potential patients who require a re-evaluation of their current ostomy products due to ongoing product issues (please refer to section 5 '*In- and exclusion criteria*'). If the patient is interested in study participation the subject must sign an informed consent after having received verbally and written information about the study. When signed the subject can undergo the screening assessment and if found eligible the subject can be enrolled in the study.

Following enrollment, the nurse will perform body profile assessment (the stoma and peristomal area) of the subject using the Body Assessment Tool. Based on the result the nurse will select the most appropriate ostomy product(s) for the subject. The body assessment tool that has been filled out for each participant will be stored in the study participant file. At the visit the subject will also be asked to evaluate the impact of leakage and fear of leakage on their QoL using the OLI-score together with recalling the number of leakage incidences the last 7 days. This questionnaire will also be stored in the study participation file. The participant

will leave the clinic with new ostomy products and be instructed to use them for the next 4-5 weeks. The participant will also receive a second questionnaire to be filled in at home after 4-5 weeks.

After 4-5 weeks, the nurse will contact the subject by phone or in a new scheduled visit to the clinic to remind the participant, if needed, to evaluate the impact of leakage on QoL/fear of leakage using the OLI score together with recalling the number of leakage incidences in the last 7 days. The subjects will send the questionnaires with a patient code directly to Coloplast. Patients will be encouraged to send in the second questionnaire even if they have discontinued using the recommended ostomy products also to know the reason for discontinuation.

After all subjects at a given study site have been included, the nurse will evaluate the Body Assessment Tool based on his/her experience of the tool in the clinic, using the Nurse Evaluation Form.

Anonymous data – including the questionnaire and the body assessment tool for each participant and the Nurse Evaluation Form will be sent to Coloplast for analysis.

5. Inclusion- and exclusion criteria

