5.3. Exclusion criteria for veterans and NPDs

The subject will not be eligible for enrollment if the subject:

- Requires a caretaker to change ostomy product(s) on the user
- Is pregnant (mainly due to substantial change of body profile during intervention)
- Is lactating (mainly due to potential weight loss and substantial change of body profile during the intervention)
- Does not have the resources personally, mentally, or physically to participate in the intervention (judged by the ostomy nurse)
- Changes his/her ostomy products (bag or plate) during the intervention period (withdraw of data)

6. Number of patients with rationale for choice

A minimum of 160 subjects will be enrolled in the study. At least 40 individuals with a stoma will be enrolled from each Nordic country (i.e. Denmark, Sweden, Norway and Finland). The subjects will be recruited from at least 3 clinics in each country and each clinic will recruit at least 5 participants to the study. The total number of participants is based on what seems feasible to enroll. As the primary endpoint will be presented using descriptive methods there is no requirements on the sample size.

The OLI score results are not the primary outcome of the study and the >160 numbers of subjects are sufficient.

7. Statistical considerations

Data from the Nurse Evaluation Form will be presented using descriptive methods.

The OLI score will be presented using both descriptive methods (i.e. sub-questions) and quantitative methods (i.e. the 3 domain scores: 'emotional impact', 'usual and social activities' and 'coping and in control').

Change of the domain scores 'emotional impact', 'usual and social activities' and 'coping and in control' and number of leakages pre-and post-transition of ostomy products will be analyzed by using paired t-test. All three domain scores are designed to range from 0-100. Higher scores represent better levels of functioning. The domain scores will be calculated as mean of the responses to each question or item within a domain (the method to estimate the domain scores is described in Appendix C).

The number of leakage episodes/7 days) will be analysed by quantitative methods (paired t-test).

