8.2. Secondary outcomes

- Rating of the user's leakage associated QoL the last 7 days (i.e. 4-point scale sub-questions) before and after ostomy product change
- Change in domain scoring of fear of leakage and the impact on QoL pre- and post-transition of ostomy product(s):
 - emotional impact
 - usual and social activities
 - coping and in control
- Number of self-reported retrospective incidences of leakage the last 7 days on prior to and after transition to more appropriate ostomy product(s)
- Analysis of connection between body profile, product solution and incidence of leakage

9. Comparison or control group

There will be no comparison to other types of products, body assessment tools or control groups.

Each subject will act as their own control when analysing the difference in the OLI score and number of leakage incidences pre-and post-transition of ostomy product(s).

10. Study follow-up schedule

No follow-up visits or contact with the users are included in the study

11. References

1. Ostomy Life Study 2019, Global Report, Data-on-file, PM-10499

12. Appendix A - Body Assessment Tool

Datum _____

Patient 3000X

Kroppsprofil

[figure not shown]
Utvärdering av den peristomala kroppsformen för att säkerställa det bästa produktvalet

1	Formen på området runt stomtin.	Platt	Området är mer eller mindre i nivå med buken, även om själva huden kan vara glömm.
		Inbuktad	Området sjunker ner i buken och bildar en grop.
		Utbuktad	Området reser sig från buken och bildar en kopp.

2	Den valda ytan kanske inte täcker hela området runt stomin	Helt	Formen täcker hela området runt stomin.
		Delvis	Formen täcker delar av området runt stomin.

3	Är magen mjuk eller fast?	Mjuk	Ytan ger vila för tryck (som motsvarar tryck på en vattenmodell).
		Fast	Ytan motstyrt tryck (som motsvarar tryck under huden).

[figure not shown]
4	Är det ytliga eller djupa veck?	Ytliga	Huden omkring stomin har linjer, dr färd eller rynkig.
		Djupa	Huden omkring stomin har djupa veck av samt rynkor.

5	Stomins placering	Över navelhöjd	Stomin är placerad över navelhöjd.

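### No step is described by which a site learns that a second questionnaire is outstanding, and the paired t-test uses only subjects with both forms

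*Combined protocol and SAP*

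**What the plan says.** All references are to the combined protocol and SAP.

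- **Baseline form (section 4).** It is completed at the clinic visit and kept in the participant's file at the site.
- **Second form (section 4).** "The participant will also receive a second questionnaire to be filled in at home after 4-5 weeks". It does not pass through the site: "The subjects will send the questionnaires with a patient code directly to Coloplast".
- **Reminder (section 4).** At 4-5 weeks the nurse contacts the subject, by phone or at a clinic visit, "to remind the participant, if needed, to evaluate the impact of leakage on QoL/fear of leakage using the OLI score". At least one phone call is planned, and on further calls the text says: "The number of phone calls will vary depending on the user's need for support".
- **Discontinuers (section 4).** They are encouraged to return the form all the same.
- **Later contact (section 10).** "No follow-up visits or contact with the users are included in the study".
- **Analysis (section 7).** The change in the three OLI domain scores and the "number of leakages pre-and post-transition of ostomy products will be analyzed by using paired t-test".
- **Missing data (Appendix C).** A domain is scored if half or more of its items are answered, and many incomplete forms are to be noted as a limitation. Nothing covers a form that never arrives or a missing leakage count.
- **Sample size (section 6).** At least 160 subjects, set by feasibility, with no allowance for non-return.

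**The concern.** The nurse can reach the subject but is not described as receiving the form or confirming that it was sent. The sponsor sees which forms arrive but identifies them by code. Section 4 describes no exchange between the two, and extra calls are tied to support needs rather than to an outstanding form. As written, a form not sent after the 4-5 week reminder stays missing.

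A paired t-test needs both values. Its result stands for all enrolled subjects only if return is unrelated to the change. Subjects who are disappointed may be less likely to post a form; so may subjects who are doing well and have lost interest. With one arm and each subject as their own control (section 9), no comparison group would show the selection. At stake are the secondary OLI and leakage results, which are the only patient-reported evidence in the study.

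**Working it through.** **The plan's own figure.** Section 6: 4 countries x 40 subjects = 160. This is an enrolment count, with no power, alpha or SD behind it.

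**Assumption.** The documents give no return rate. Return rates r of 90%, 80%, 70% and 60% are used below, and all 160 are treated as one analysis set for illustration.

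**Step 1: pairs and bias.** Pairs = 160 x r. Let the gap be the mean change in returners minus that in non-returners. The mean over all subjects is r x (returners' mean) + (1 - r) x (non-returners' mean), so

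bias of the returners' mean = (1 - r) x gap.

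| r | pairs | lost | bias as share of gap |
|---|---|---|---|
| 90% | 144 | 16 | 10% |
| 80% | 128 | 32 | 20% |
| 70% | 112 | 48 | 30% |
| 60% | 96 | 64 | 40% |

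**Step 2: return related to the unseen change (assumed values).** Returners improve by 12 points, non-returners by 0. The mean for all is 12 x 0.9 = 10.8 down to 12 x 0.6 = 7.2. The reported 12 is too high by 1/0.9 - 1 = 11% up to 1/0.6 - 1 = 67%.

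**Step 3: return related to baseline only (assumed values).** If the follow-up score has slope b on baseline, the bias of the complete-pair change is

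(1 - b) x (baseline mean of all - baseline mean of returners).

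With b = 0.5 and returners 5 points better at baseline: 0.5 x (-5) = -2.5. The reported change is now 2.5 points too small, the opposite direction to step 2.

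**Step 4: effect on the test.** Assume a two-sided 0.05 test, a true mean change of zero over all subjects, and a gap of 0.5 SD of the change. The returners' mean is then 0.5 x (1 - r) SD = 0.05, 0.10, 0.15 and 0.20 SD. Multiplied by the square root of the number of pairs, and by normal approximation, this gives rejection probabilities of 0.092, 0.205, 0.355 and 0.500. With a gap of 0.25 SD they are 0.060, 0.087, 0.125 and 0.165.

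**Step 5: precision.** The change detectable with 80% power is (1.960 + 0.842)/sqrt(pairs): 0.22 SD with 160 pairs and 0.29 SD with 96. The loss is small. The issue is selection, and more enrolment would not remove it.

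**Step 6: what a model can and cannot correct.** A likelihood-based repeated-measures model with all baselines predicts a non-returner's follow-up from returners with the same baseline. That removes the bias in step 3. In step 2, if both groups have the same baseline distribution, the prediction for non-returners is again a gain of 12, so the model also reports 12 against 10.8 to 7.2. Setting non-returners to no change gives r x 12 = 10.8 to 7.2, which is correct there because the assumption matches the scenario.

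**The case against.** The strongest reply has four parts.

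**Safeguards exist.** The reminder is personal and timed to the due date, it may be a clinic visit, at least one call is planned, and discontinuers are encouraged to respond. This stands and should lower the number of missing forms. It does not identify a form that is still missing afterwards. A discontinuer who has moved to another product is in any case removed from the final data under section 7.

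**Silence is not prohibition.** A reader might infer that nobody able to reach a subject could ever find out that a form is missing. The documents do not support that. The forms carry a code, the body assessment form in Appendix A has a patient number field and is kept in the participant's file, and nothing bars the sponsor from telling a site which codes are outstanding. What the text supports is that no such step is described.

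**The before and after item tables may be on the same people.** A reader might infer that the OLI sub-questions will be tabulated on all subjects before and on returners only after. Section 7 does not say so, and section 9 makes each subject their own control. That inference is conjecture and is not part of this point.

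**The endpoints are secondary.** The primary outcome comes from the Nurse Evaluation Form and does not depend on the second questionnaire. The OLI objective is worded as exploratory. This stands and sets the weight of the point.

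**Conclusion.** The point holds as a minor one. The plan describes no way for a site to learn that a second form is outstanding, has no rule for a form that never arrives, and uses an analysis that leaves out every non-returner. The secondary OLI and leakage changes can therefore be those of a self-selected subset.

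The size rests on assumptions. With 10% to 40% non-return the bias is 10% to 40% of the gap in mean change between returners and non-returners, and that gap is not known. It would be tempting to conclude that the reported improvement will be too large, by 11% to 67%. That follows only from the assumed 12-against-0 scenario; the baseline-related scenario points the other way, and the documents decide neither. It would be equally tempting to conclude that a repeated-measures model in place of the t-test settles the matter. It corrects only return that depends on observed baseline.

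**What to change.** **Section 4.** The sponsor periodically sends each site the codes for which no second form has arrived, and the nurse gives those subjects one further reminder within a stated time window. The date of completion is recorded on the form, because the questions cover the last 7 days and a late form describes a later week.

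**Section 10.** Reword it so that this contact is allowed.

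**Section 7.** Keep the paired t-test and add beside it:
- a likelihood-based repeated-measures model that includes the baseline of all enrolled subjects, with the statement that it corrects only for return depending on observed baseline;
- a sensitivity analysis with non-returners set to no change, for return related to the unseen change, described as an assumption rather than a bound, since non-returners could also have worsened;
- the numbers enrolled, returned and analysed, with baseline OLI scores and leakage counts of returners and non-returners.

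**Cost.** Code lists across 20 to 40 sites, one extra reminder for some subjects, and a few lines of analysis. Some forms will be completed slightly late. If the returners improve, the no-change result will be less favourable than the t-test. No change to the sample size follows, because no return rate is given.

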The exploratory NPD data from the clinical site Meilahden tornisairaala, Finland will not be pooled with the veteran data as the two groups can be potentially very different in the change of peristomal body profiles during the study period. This makes the two groups less comparable and the NPD data will therefore be analysed separately.

There will be no comparison to other types of products or body assessment tools. In case subjects change to other ostomy products during the intervention period the data of the given subject will not be included in the final data of the study.

8. Primary and secondary outcomes

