8.1. Primary outcome

- The usability of the Body Assessment Tool will be based on the Nurse Evaluation Form including the following questions (evaluation performed by the nurse) (6-point scale):
 - How well does the Body Assessment Tool work in a clinical setting?
 - How well does the assessment of the user's body profile work prior to selecting ostomy product(s)?
 - Do you experience that the Body Assessment Tool supports you to increase the quality of the treatment?

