		I navelhöjd	Stomin är placerad i navelhöjd.
		Under navelhöjd	Stomin är placerad under navelhöjd.

6	Stomimynningens placering i förhållande till huden	Över hudplanet	Stomimynningen är över hudplanet.
		I nivå med hudplanet	Stomimynningen är i nivå med hudplanet.
		Under hudplanet	Stomimynningen är under hudplanet.

Konsistensen på det som kommer ut från stomin

Konsistans:	Tjock avförling	
	Lös avförling	
	Urin	

Val av produkt

Typ av häfta	Typ av system	Typ av påse
Platt	1-delssystem	Tömbar påse
Convex Soft	2-delssystem (klick/mekanisk koppling)	Sluton påse
Convex Light	2-delssystem (haftkoppling)	Urostomipåse
Convex Deep		
Konkav		
Annat		

Tillbehörsprodukter

Övriga faktorer som har haft betydelse vid val av produkt (markera gärna med flera kryss)

Den peristomala huden	Patientens tillgång till hjälp i hemmet
Patientens allmänna tillstånd	Patientens förmågor

©Coloplast AB, Coloplast Care / Ostomy Care / Wound & Skin Care / Interventional Urology

Coloplast AB, [name], Sweden.
www.coloplast.se Coloplast är ett registered varumärke, dit är Coloplast AB. © 2020-08. Alla rättigheter tillvarat Coloplast AB.

13. Appendix B - Nurse Evaluation Tool

Utvärdering

Nordisk Konsensus Studie

Sjukhus: _____

Avdelning: _____

Stomiterapeut: _____

Datum: _____

1	Hur många stomiopererade har deltagit i studien? _____					
2	Hur väl upplever du att verktyget Kroppsprofil fungerar i klinisk praxis (där 6 är bäst). Markera med x					
	1 	2 	3 	4 	5 	6 
3	Hur väl upplever du att det fungerar att utgå ifrån patientens kroppsprofil, när du ska välja stomiprodkuter? (där 6 är bäst). Markera med x					
	1 	2 	3 	4 	5 	6 
4	Upplever du att verktyget Kroppsprofil hjälper till att lyfta kvaliteten på behandlingen? (där 6 är bäst). Markera med x					
	1 	2 	3 	4 	5 	6 

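### If the single NPD site also enrols veterans, a nurse who sees both groups gives one blended usability rating, which cannot be kept separate as section 7 requires

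*Combined protocol and SAP*

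**What the plan says.** All references are to the combined protocol and SAP.

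- **Why NPDs are recruited.** The background text before section 2 says "it is of interest to explore usability of The Body Assessment Tool in the group of newly stoma patients", and continues: "A subgroup of NPDs will therefore be recruited at one clinical site".
- **How usability is measured.** Section 8.1: "The usability of the Body Assessment Tool will be based on the Nurse Evaluation Form including the following questions". Three questions follow, each on a 6-point scale. Section 3.1 names no other usability instrument.
- **When the form is completed.** Section 4: "After all subjects at a given study site have been included, the nurse will evaluate the Body Assessment Tool". The evaluation rests on the nurse's experience of the tool in the clinic. Section 4 also puts NPDs through the same procedures as veterans and describes no separate nurse evaluation for them.
- **What the form records.** Appendix B has lines for hospital, department, stoma therapist and date. Item 1 asks for one total number of participants: "Hur många stomiopererade har deltagit i studien". Items 2-4 take one rating each; item 2, for example, asks how well the tool works in practice: "Hur väl upplever du att verktyget Kroppsprofil fungerar i klinisk praxis (där 6 är bäst". Item 5 is a tally of four other factors, item 6 is free text, and item 7 is a yes/no recommendation with a reason. No item refers to veterans or NPDs.
- **How the groups are to be handled.** Section 7 says the NPD data "will not be pooled with the veteran data as the two groups can be potentially very different", and that "the NPD data will therefore be analysed separately".

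**The concern.** The subgroup was added because usability in new stoma patients is of interest, and the analysis plan keeps the two groups apart. The only usability instrument, however, gathers a nurse's whole experience into single answers and has nowhere to record which group they refer to. If one nurse has used the tool in both groups, section 7 cannot be followed for the primary outcome.

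This is a data-collection gap. Once a blended rating has been given, no analysis can undo it. What is at stake is mainly the NPD usability result, which would have no numeric data of its own. To a much smaller degree the main usability summary is affected, because it would contain some NPD experience.

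**Working it through.** The plan gives no figure to reproduce. The check sets the texts against each other and then bounds the size.

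**1. Can a blended rating be split?** Write the nurse's answer to any of items 2-4 as R = wV + (1 − w)N, where V is the rating the nurse would give for veterans, N the rating for NPDs, and w the unstated weight given to veterans. The form returns R only. Even if w were taken as the veterans' share of participants at the site, this is one equation in two unknowns. Item 7 is a single yes/no and cannot be divided either.

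**2. Can the item 5 tallies be split?** Yes. Item 5 asks the nurse to copy counts from the completed Body Assessment Tools. Those are filled in per participant, carry a patient number (Appendix A) and go to the sponsor (section 4). Analysing the OLI and leakage data separately already requires each participant's group to be known, so the tallies can be recounted by group.

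**3. Does the situation arise?** It depends on enrolment at the NPD site:

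| NPD site enrols | Items 2-4 and 7 | Item 5 | Compatible with section 7? |
|---|---|---|---|
| NPDs only | Identifiable from the hospital line | Identifiable | Yes, if that form is kept out of the veteran summary |
| Both, with each nurse seeing one group | Separable only if each nurse's group is recorded | Can be recounted | Only with that record |
| Both, with a nurse seeing both groups | Blended | Can be recounted | No |

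The background text and section 7 identify the NPD data by one hospital but do not say who else is recruited there. The eligibility lists in section 5 and the minimum numbers per clinic in section 6 do not settle it.

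**4. Size for the main usability summary.** Inputs: 20 to 40 sites (section 4); at least 3 clinics in each of 4 countries (section 6), so at least 3 × 4 = 12; ratings from 1 to 6 (Appendix B). Assumption: one form per site.

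- Share of forms affected = 1/n.
- Adding one form with rating x to n − 1 forms with mean m moves the mean by (x − m)/n, which is at most (6 − 1)/n = 5/n.

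| n forms | Share affected | Largest shift in a mean rating |
|---|---|---|
| 40 | 1/40 = 2.5% | 5/40 = 0.125 |
| 20 | 1/20 = 5% | 5/20 = 0.25 |
| 12 | 1/12 = 8.3% | 5/12 = 0.42 |

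These are ceilings. Reaching them needs a form at one end of the scale and all others at the opposite end.

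**5. Size for the NPD subgroup.** Under the same assumption, the site's one form is the subgroup's entire set of usability ratings. If it is blended, there are no separable numeric ratings.

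**The case against.** **Mixed enrolment is not stated.** This stands. If the site takes only NPDs, the hospital line already separates its form. What remains is smaller: section 8.1 does not restrict the primary outcome to veteran forms, and nothing says explicitly that this site's form stays out of the main summary.

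**The no-pooling rule may be meant for patient-reported outcomes only.** Its reason is a differing change in peristomal body profile over the study period, which fits before/after scores more naturally than a nurse's opinion of a tool used at one visit. This is a fair reading. Against it, section 7 speaks of NPD data without exception, and the background gives the same body-profile reason for wanting usability data in NPDs.

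**Section 4 fixes timing, not one form per site.** This also stands. The therapist and department lines allow several forms from one site. That separates the groups only if each nurse treated one group, which the plan does not require.

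**The consequence is small.** NPD usability is named in the background but not among the objectives or outcomes. NPD data are exploratory, usability is descriptive, and no test or decision rule is touched. All of this is correct and limits the weight of the point.

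**The Finnish form is not shown.** Appendix B is in Swedish. Since NPDs follow the same protocol, a plain translation is likely, but that is an assumption.

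**Conclusion.** The point holds conditionally. If the NPD site also enrols veterans and a nurse there treats both groups, items 2-4 and 7 on that nurse's form cannot be assigned to either group. This conflicts with section 7 as written and leaves no separable numeric usability result for NPDs. It assumes that section 7 covers nurse ratings and that the Finnish form has the same content as Appendix B.

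A reader might infer more than the documents support:

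- *That section 7 is certain to be breached.* Mixed enrolment is neither stated nor excluded.
- *That the item 5 tallies are lost.* They can be recounted from the per-participant tools.
- *That nothing at all would be known about usability in NPDs.* A nurse could describe it in the item 6 free text; the numeric ratings are what would be missing.
- *That the main usability result is compromised.* Assuming one form per site, about 1 of 20-40 forms is involved, with a shift of at most 0.125-0.25 points.

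The change is still worth making before the site completes its forms, because it costs little and the blend cannot be undone.

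**What to change.** State in section 4 whether the NPD site enrols veterans.

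- **If it does:** each nurse who sees both groups completes one Nurse Evaluation Form per group, marked with the group and with that group's number of participants in item 1. A nurse who sees one group marks the form with that group.
- **If it enrols only NPDs:** its form is reported separately.
- **In both cases:** state in sections 7 and 8.1 that only veteran forms enter the main usability summary, and that NPD forms are described on their own, without comparison, in line with section 4.

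The cost is a few lines of text and, at a mixed site, one extra short form for each nurse who sees both groups. The downside is that two ratings from the same nurse may influence each other, so the NPD ratings should be read with that in mind.
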